7.2.3. Duration of Response

Duration of response will be assessed by RECIST v1.1.

Censoring of DOR will follow the same algorithm as the censoring of PFS. The KM estimate of median DOR will be presented with its 95% CI. The 95% CI will be calculated using Brookmeyer and Crowley's method ([1982](#)).

7.2.4. Largest Percentage Reduction in Sum of Diameters of Target Lesions

For each subject in the response evaluable population with target lesions at baseline, target lesion sizes will be measured by sum of diameters. The best percent change from baseline, defined as the largest decrease in target lesion size for each subject, will be summarized descriptively.

Per RECIST v1.1, target lesions considered "too small to measure" will be assigned a default value of 5 mm for purposes of this analysis. Likewise, target lesions identified as "not present" at postbaseline assessments will be assigned 0 mm for this analysis. In the event a target lesion is unaccounted for in a particular postbaseline timepoint (ie, assessment missing or NE), then the overall sum of diameters for target lesions will not be evaluable for that postbaseline timepoint.

7.2.5. Progression-Free Survival

Progression-free survival will be assessed by RECIST v1.1.

[figure not shown]
Censoring for PFS will follow the algorithm outlined in [Table 12](#), which is based on the FDA Guidance for Industry: Clinical Trial Endpoints for the Approval of Cancer Drugs and Biologics ([FDA 2007](#)).

The KM estimate of median PFS will be presented with its 95% CI. The 95% CI will be calculated using Brookmeyer and Crowley's method (1982).

Table 12: Evaluation and Censoring of Progression-Free Survival

Situation	Outcome	Date of Progression or Censoring
No baseline tumor assessments	Censored	Date of Day 1
No valid postbaseline response assessments	Censored	Date of Day 1
Progression documented between scheduled response assessments	Progressed	Date of first overall response of PD
No progression	Censored	Date of last valid radiologic assessment (not NE and not missing)
Study discontinuation for undocumented progression	Censored	Date of last valid radiologic assessment (not NE and not missing)
Study discontinuation for toxicity or other reason	Censored	Date of last valid radiologic assessment (not NE and not missing)
New anticancer treatment started	Censored	Date of last valid radiologic assessment (not NE and not missing) on/before starting a new anticancer treatment.
Death before first progressive response assessment	Progressed	Date of death
Death between adequate response assessments	Progressed	Date of death
Death or progression after more than 1 missed assessment	Censored	Date of last valid radiologic assessment (not NE and not missing) prior to death

Under RECIST v1.1, PFS is defined as the length of time between the baseline visit (Day 1) and the earlier of death or first assessment of PD. Date of death will be determined using the Death Report, Survival Follow-Up, and Subject Status eCRFs.

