5.4.2. Treatment After Initial Evidence of Radiographic Disease Progression

Immunotherapeutic agents such as pembrolizumab and epacadostat may produce antitumor effects by potentiating endogenous cancer-specific immune responses. The response patterns seen with such an approach may extend beyond the typical time course of responses seen with cytotoxic agents and can manifest as a clinical response after an initial increase in tumor burden or even the appearance of new lesions.

If radiographic imaging shows PD, tumor assessment should be repeated 2 to 4 weeks and no later than 8 weeks after the initial assessment to confirm PD, with the option of continuing treatment as outlined below, while awaiting radiographic confirmation of progression. If repeat imaging shows a reduction in the tumor burden compared to the initial scan demonstrating PD, treatment may be continued as per treatment calendar. If repeat imaging confirms PD, subjects will be discontinued from study therapy. In determining whether the tumor burden has increased or decreased, investigators should consider all target lesions as well as nontarget lesions.

When feasible, subjects should not be discontinued until progression is confirmed; however, the decision to continue study treatment after the first evidence of disease progression is at the investigator's discretion based on the clinical status of the subject as described in [Table 26](#).

Subjects may receive study treatment while waiting for confirmation of PD if they are clinically stable as defined by the following criteria:

- Absence of signs and symptoms (including worsening of laboratory values) indicating disease progression.
- No decline in ECOG performance status.
- Absence of rapid progression of disease.
- Absence of progressive tumor at critical anatomical sites (eg, cord compression) requiring urgent alternative medical intervention.

Table 26: Imaging and Treatment After First Radiographic Evidence of Progressive Disease

	Clinically Stable		Clinically Unstable	
	Imaging	Treatment	Imaging	Treatment
First radiographic evidence of PD	Repeat imaging at 4 and 8 weeks to confirm PD	May continue study treatment at the investigator's discretion while awaiting confirmatory scan	Repeat imaging at 4 and 8 weeks to confirm PD if possible	Discontinue treatment
Repeat scan at 4 and 8 weeks confirms PD	No additional imaging required	Discontinue treatment	No additional imaging required	N/A

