7.6.1.2. Tumor Imaging During the Study

Tumor imaging may be performed by CT or MRI, but the same imaging technique should be used in a subject throughout the study. Scans must be a contrast CT or MRI, except in circumstances where there is a contrast allergy or with medical monitor approval. A PET/CT scan that uses higher energy and thinner slices for the CT component may be acceptable (with medical monitor approval) if it was the same technique used for baseline. Imaging should be performed every 9 weeks (63 days \pm 7 days) or more frequently if clinically indicated. After 12 months of study treatment, imaging frequency may be reduced to every 12 weeks. Imaging should not be delayed for delays in cycle starts or extension of combination treatment cycle intervals.

Imaging should continue to be performed until documented disease progression, the start of new anticancer treatment, withdrawal of consent, death, or the end of the study, whichever occurs first. Disease progression should be confirmed at least 4 weeks and not later than 8 weeks after the first scan indicating PD in clinically stable subjects. Subjects who have unconfirmed disease progression may continue on treatment until progression is confirmed provided that they have met the conditions detailed in Section 7.6.1.

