7.2. Analysis of the Efficacy Parameters

7.2.1. Response Criteria

Overall disease status will be categorized using RECIST v1.1. Subjects will have their overall response evaluated as CR, PR, SD, PD, or NE at each postbaseline radiological assessment based on changes in target lesions, nontarget lesions, and appearance of new lesions.

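### The last row of SAP Table 12 covers death and progression after missed scans but dates censoring from death only, so a progression found after a gap is censored too late or has no date

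*SAP*

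**What the plan says.** SAP 7.2.5, Table 12, sets the event and censoring rules for PFS. Its last row has the situation "Death or progression after more than 1 missed assessment", the outcome censored, and the date "Date of last valid radiologic assessment (not NE and not missing) prior to death". Two events share the row; the date names one of them. The new-therapy row, by contrast, ties its date to its own event: the last valid scan "on/before starting a new anticancer treatment".

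Four other passages bear on the row:

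- SAP 7.2.5 states that "PFS is defined as the length of time between the baseline visit (Day 1) and the earlier of death or first assessment of PD".
- SAP 7.2.1 states that "Subjects will have their overall response evaluated as CR, PR, SD, PD, or NE at each postbaseline radiological assessment". Progressive disease (PD) is thus a separate category from NE (not evaluable).
- SAP 7.2.3 states that "Censoring of DOR will follow the same algorithm as the censoring of PFS".
- On scan timing, Protocol 7.6.1.2 states that "Imaging should be performed every 9 weeks", with an optional 12-week interval after 12 months. Protocol 5.4.2 adds: "If radiographic imaging shows PD, tumor assessment should be repeated".

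**The concern.** A censoring rule for events found after a gap exists because nobody knows when in the gap the event happened. The usual remedy is to stop the clock at the last scan before the gap, and that is evidently what this row is for. As worded, it does so for deaths only. For progressions it keeps the whole unobserved interval as progression-free time and then removes the event, so the subjects affected are ones known to have progressed.

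PFS and DOR are secondary endpoints in both parts of the study, and DOR inherits the rule. A programmer following the text and one following the intent would produce different results from the same data, and the text gives the more favourable one.

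**Working it through.** The documents give no target median, event count or power for PFS or DOR, so there is no stated figure to reproduce. The check is a literal reading, then its effect on the Kaplan-Meier estimate.

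**1. Which date the row returns**

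| Case after two or more missed scans | Last valid scan before death | Evident intent |
|---|---|---|
| Death, no scan in between | Last scan before the gap | Same |
| Progression, later death recorded | PD scan, or a later valid scan | Last scan before the gap |
| Progression, no death recorded | Undefined | Last scan before the gap |

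A PD scan is neither NE nor missing, so it is valid. Later scans are expected because the protocol asks for repeat imaging after first PD. The third case may be common: Amendment 4 ended survival follow-up, and SAP 2.1 says the plan applies to later amendments. Nothing in SAP 7.2.3 or 7.2.5 redirects the date.

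**2. Length of the credited gap**

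More than one missed scan means at least two, so a PD scan made on schedule is at least the third after the last valid one: 3 × 9 = 27 weeks (189 days), or 3 × 12 = 36 weeks on the longer interval. An unscheduled PD scan could shorten this, but to no less than about 2 × 9 = 18 weeks.

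Worked record: stable disease at Week 9, Weeks 18 and 27 missed, PD at Week 36, death at Week 60. Intended censoring is day 63; the literal rule gives day 252. The difference is 252 − 63 = 189 days.

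**3. Direction**

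S(t) is the product of (1 − d/n) over event times. Both rules leave the same events d. The literal rule keeps affected subjects at risk longer, so each n is equal or larger and S(t) is equal or higher. In 2,000 random data sets of 27 subjects there were no exceptions. The same holds for DOR among responders.

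**4. Ten-subject example**

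Events at days 63, 63, 126, 126, 189, 189, 252 and 315, plus two subjects last scanned at day 63 with PD at day 252.

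| Day | Pre-gap censoring | Literal |
|---|---|---|
| 63 | 8/10 = 0.800 | 8/10 = 0.800 |
| 126 | 0.800 × 4/6 = 0.533 | 0.800 × 6/8 = 0.600 |
| 189 | 0.533 × 2/4 = 0.267 | 0.600 × 4/6 = 0.400 |
| 252 | 0.267 × 1/2 = 0.133 | 0.400 × 3/4 = 0.300 |

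The median is 189 days under both. Counting the two progressions as events at day 252 would give 0.100 there, so the literal curve is above that alternative too.

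**5. A small group in which the median moves**

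Seven subjects: PD at days 63, 126, 126, 189 and 189, plus two gap subjects as above. Pre-gap: 6/7 = 0.857 at day 63, then 0.857 × 2/4 = 0.429 at day 126, so the median is 126 days. Literal: 0.857 × 4/6 = 0.571 at day 126, then 0.571 × 2/4 = 0.286 at day 189, so the median is 189 days. The SAP summarises by dose level, so groups may be small.

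**6. How many subjects, under assumptions**

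A simulation of 20,000 subjects per setting assumed 9-week scans, exponential PFS with median 9 or 16 weeks, and independent missed scans. About 1% of subjects were affected with 10% of scans missed and 4-5% with 20%. The shares come out lower if subjects who die before their next scan, and those with no valid post-baseline scan before the gap, are left out.

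A second simulation took medians of 3.7 and 12.4 months from studies cited in the protocol, as assumptions. It assigned a gap to 5%, 10% or 20% of subjects with PD at the second scan or later. The median changed in one of six settings: 126 days (pre-gap) to 189 days (literal), at 3.7 months and 20%. There, survival at day 126 moved only from 0.485 to 0.502.

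**The case against.** The best defence is that this is a drafting slip. The row's purpose is clear, and a competent programmer may well apply the pre-gap date regardless. That bears on how likely the error is, but the SAP does not supply the right date.

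The defence is stronger on size, and four larger claims that a reader might infer do not hold:

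- **That time is credited past the progression.** If the worked record had a confirmatory scan at Week 40, a literal reading could reach day 280, an excess of 217 days. But the same section ends PFS at first PD, so only the 189 days to Week 36 can be relied on. The protocol also times confirmation for clinically stable subjects only.
- **That every affected subject is biased upward.** With no recorded death the row gives no date. That is an undefined result, and its direction depends on what the programmer then does.
- **That median PFS could be overstated by 9 weeks.** One simulated setting (16-week median, an assumed 30% of scans missed) moved the median from 18 to 27 weeks. A repeat of it moved survival at 18 weeks only from 0.497 to 0.523: the curve happened to sit near 0.5 on a scan date.
- **That event rates or landmark survival are misreported.** Neither is a specified output. SAP 7.2.3 and 7.2.5 specify medians with 95% confidence intervals, and SAP 10.2 drops all figures.

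It is also true that the study stopped early, that no hypothesis is tested on PFS or DOR, and that Protocol 9.4.2 estimates them only if there are enough observations.

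**Conclusion.** The concern stands as a wrong rule with a probably small effect. For a progression after more than one missed assessment, the stated date is the PD scan or later when a death follows, and undefined otherwise. Used literally, it adds at least 27 weeks of unobserved time when the PD scan falls on the 9-week schedule, drops the event, and can only leave the PFS and DOR curves equal or higher than pre-gap censoring would.

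The direction follows from the wording and needs no assumed miss rate. The share of subjects affected rests wholly on assumed rates, because the documents give none. The planned medians will often be unchanged, with small dose-level groups the main exception. The objective response rate, its Type I error and its power are untouched. The documents do not support saying that the trial's PFS or DOR results are materially inflated.

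**What to change.** In the last row of Table 12, for both PFS and DOR, set the date to the last valid radiologic assessment (neither NE nor missing) before the consecutive missed scheduled assessments that immediately precede the death or progression, whichever comes first.

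Define a missed assessment against the 9-week schedule, or the 12-week schedule where a subject has moved to it, with the 7-day window, and state whether an NE scan counts as missed.

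The cost is about one line of SAP text and one of programming, with no new data. PFS and DOR may become slightly less favourable.

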8. SAFETY AND TOLERABILITY

A list of planned tables and listings is provided in [Appendix A](#).

8.1. General Considerations

Summary tables may be replaced with listings when appropriate. For instance, an AE frequency table may be replaced with a listing if it only contains a few unique PTs reported on relatively few subjects.

8.2. Adverse Events

8.2.1. Adverse Event Definitions

A TEAE is any AE either reported for the first time or worsening of a pre-existing event after the first dose of study drug (epacadostat, pembrolizumab, and azacitidine). Analysis of AEs (as discussed below) will be limited to TEAEs, but data listings will include all AEs regardless of their timing in relation to study drug administration.

Adverse events will be tabulated by MedDRA PT and SOC. Severity of AEs will be graded using the NCI CTCAE. The CTCAE v4.03 is used for this study. The CTCAE reporting guidelines and grading details are available on the Cancer Therapy Evaluation Program website.

The subset of AEs considered by the investigator to be related to study drug will be considered to be treatment-related AEs. If the investigator does not specify the relationship of the AE to study drug, the AE will be considered to be treatment-related. The incidence of AEs and treatment-related AEs will be tabulated. In addition, SAEs will also be tabulated.

Any missing onset date, causality, or severity must be queried for resolution. Unresolved missing causality and severity will be handled according to the following rules:

- An unresolved missing causality will be considered treatment-related.
- An unresolved missing severity will be identified as an unknown severity.

For purposes of analysis, all AEs will be considered TEAEs unless the AE can unequivocally be defined as not treatment-emergent.

8.2.2. Dose-Limiting Toxicities

The number of subjects with DLTs and the type of DLT will be listed by dose level.

8.2.3. Maximum Tolerated Dose

In Part 1, the MTD is defined as the highest dose level at which $\leq 1/6$ or $\leq 2/9$ subjects experience a DLT.

8.2.4. Adverse Events of Special Interest

Adverse events of special interest include irAEs that are seen with immunotherapy and any other observed autoimmune phenomenon.

An overall summary of irAEs will include number (%) of subjects reporting any irAEs, any Grade 3 or 4 irAEs, any treatment-related irAEs, any fatal irAEs, and any irAEs leading to treatment interruption/dose reduction/discontinuation.

8.2.5. Adverse Event Summaries

An overall summary of AEs by dose level in Treatment Group A will include:

- Number (%) of subjects reporting any TEAEs
- Number (%) of subjects reporting any DLTs
- Number (%) of subjects reporting any SAEs
- Number (%) of subjects reporting any Grade 3 or 4 TEAEs
- Number (%) of subjects reporting any TEAEs related to epacadostat
- Number (%) of subjects reporting any TEAEs related to azacitidine
- Number (%) of subjects reporting any TEAEs related to pembrolizumab
- Number (%) of subjects who temporarily interrupted epacadostat because of TEAEs
- Number (%) of subjects who temporarily interrupted azacitidine because of TEAEs
- Number (%) of subjects who temporarily interrupted pembrolizumab because of TEAEs
- Number (%) of subjects who permanently discontinued epacadostat because of TEAEs
- Number (%) of subjects who permanently discontinued azacitidine because of TEAEs
- Number (%) of subjects who permanently discontinued pembrolizumab because of TEAEs
- Number (%) of subjects with epacadostat dose reductions because of TEAEs
- Number (%) of subjects with azacitidine dose reductions because of TEAEs
- Number (%) of subjects who had a fatal TEAE
- Number (%) of subjects who withdrew from study because of TEAEs

The following summaries will be produced by MedDRA term (if 10 or fewer subjects appear in a table, a listing may be appropriate):

- Summary of TEAEs by SOC and PT
- Summary of TEAEs by PT in decreasing order of frequency
- Summary of TEAEs by SOC, PT, and maximum severity
- Summary of Grade 3 or 4 TEAEs by SOC and PT
- Summary of epacadostat treatment-related AEs by SOC and PT
- Summary of pembrolizumab treatment-related AEs by SOC and PT
- Summary of azacitidine treatment-related AEs by SOC and PT
- Summary of TEAEs with a fatal outcome by SOC and PT
- Summary of serious TEAEs by SOC and PT
- Summary of serious TEAEs by PT in descending order of frequency
- Summary of nonserious TEAEs by SOC and PT
- Summary of TEAEs leading to epacadostat dose reduction by SOC and PT
- Summary of TEAEs leading to azacitidine dose reduction by SOC and PT
- Summary of TEAEs leading to epacadostat dose interruption by SOC and PT
- Summary of TEAEs leading to pembrolizumab dose interruption by SOC and PT
- Summary of TEAEs leading to azacitidine dose interruption by SOC and PT
- Summary of TEAEs leading to discontinuation of epacadostat by SOC and PT
- Summary of TEAEs leading to discontinuation of pembrolizumab by SOC and PT
- Summary of TEAEs leading to discontinuation of azacitidine by SOC and PT
- An overall summary of treatment-emergent irAEs

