5.4.1.1. Dose-Limiting Toxicity and Determination of Maximum Tolerated Dose

A DLT will be defined as the occurrence of any of the toxicities in Table 10 occurring up to and including Day 21 for Treatment Group A or Day 42 for Treatment Groups Band C. Only toxicities with a clear alternative explanation (eg, due to disease progression), transient (72 hours) abnormal laboratory values without associated clinically significant signs or symptoms based on investigator determination, irAEs of Grade 3 or higher that improve to Grade 1 or lower in < 5 days by appropriate care or with corticosteroid therapy can be deemed a non-DLT. All DLTs will be assessed by the investigator using the current CTCAE v4.03 criteria. Subjects who receive 2:75% doses of study drug (Treatment Group A: azacitidine [4 doses], epacadostat [32 doses], and pembrolizumab [1 dose]; Treatment Group B: INCB057643 [32 doses], epacadostat [32 doses], and pembrolizumab [1 dose]; Treatment Group C: INCB059872 [QD dosing, 32 doses; QoD dosing, 16 doses], epacadostat [32 doses], and pembrolizumab [1 dose]) at the level assigned or have a DLT will be considered evaluable for determining tolerability of the dose.

Individual subject dose reductions may be made based on events observed at any time during treatment with study drug; however, for the purposes of dose cohort escalation/de-escalation, expanding a dose cohort, and determining the MTD of the study drugs, decisions will be made based on events that are observed from the first day of study drug administration through and including the final day of Cycle 1 (Day 21) for Treatment Group A or Cycle 2 (Day 42) for Treatment Groups B and C. A lower MTD may subsequently be determined based on relevant toxicities that become evident after Day 21 (Treatment Group A) or Day 42 (Treatment Groups Band C).

Table 10: Definition of Dose-Limiting Toxicity

Toxicity

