3.1.2. Dose-Escalation Phase (All Treatment Groups)

A 3 + 3 + 3 design will be used to assess the MTD, maximum tested dose, or PAD of the triplet combination of azacitidine, INCB057643, or INCB059872 with pembrolizumab and epacadostat in 21-day treatment cycles. The MTD will be defined as the highest dose at which less than one-third of the subjects (with a minimum of 6 subjects) have a DLT. When the MTD, maximum tested dose, or PAD has been determined or reached, the dose will be recommended for Part 2. The Part 2 expansion will begin after the determination of the MTD, maximum tested dose, or PAD; however, enrollment priority will be given to the open Part 1 dose-escalation cohort.

A minimum of 3 subjects will initially be enrolled in Cohort 1, and each subject will be observed for 21 days from the start of triplet combination therapy before enrollment in the next cohort begins. The dose of azacitidine, INCB057643, or INCB059872 (or epacadostat) will be escalated if 0 of the first 3 evaluable subjects enrolled has a DLT. If 1 of 3 subjects in Cohort 1 has a DLT, the cohort will be expanded to 6 subjects. If 1 of 6 subjects in Cohort 1 has a DLT, a new cohort of 3 subjects will be treated at the next higher dose level (Cohort 2). If 2 of 6 subjects in Cohort 1 have a DLT, that cohort will be further expanded to a total of 9 subjects. If $\leq 2/9$ subjects have a DLT, 3 subjects will be treated at the next higher dose level. If $\geq 2/3$, $3/6$, or $3/9$ subjects have a DLT within a cohort, dose de-escalation will be required, and Cohorts -1 or -2 will be tested. The MTD is defined as the highest dose level at which $\leq 1/6$ or $\leq 2/9$ subjects experience a DLT.

Subjects must have received $\geq 75\%$ of planned doses of study drug during the 21-day DLT (Treatment Group A) or 42-day DLT (Treatment Groups B and C) observation period or have had a DLT to be evaluable for dose tolerability (Treatment Group A: azacitidine [4 doses], epacadostat [32 doses], and pembrolizumab [1 dose]; Treatment Group B: INCB057643 [32 doses], epacadostat [32 doses], and pembrolizumab [1 dose]; Treatment Group C: INCB059872 [QD dosing, 32 doses; QoD dosing, 16 doses], epacadostat [32 doses], and pembrolizumab [1 dose]).

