3.1.3.1.2. Treatment Group A Treatment Sequencing Tumor Biopsy Cohorts (Part 2)

The sequencing biopsy cohorts require 3 tumor biopsies to identify epigenetic changes and changes in the tumor microenvironment induced by each of the components of the regimen. All subjects will have tumor biopsies at baseline and 2 additional biopsies while on study treatment.

Approximately 25 subjects will be enrolled in Expansion Cohorts A-3 and A-4, and approximately 10 subjects will be enrolled in Expansion Cohort A-5. The eligible tumor types for Expansion Cohorts A-3, A-4, and A-5 are HNSCC, melanoma, UC, and MSS CRC. In Expansion Cohorts A-3 and A-4, subjects with tumor types other than MSS CRC must have had disease progression on a prior PD-1 pathway-targeted agent.

Five to 8 evaluable subjects per tumor type in Expansion Cohorts A-3 and A-4, and 10 subjects in Expansion Cohort A-5 will initiate treatment and have tumor biopsies performed as indicated in [Table 5](#).

Table 5: Treatment Group A Treatment Sequencing Tumor Biopsy Cohorts (Part 2)

Cohort	Treatment Sequence	Biopsy Sequence	Tumor Type (n)
Expansion Group A-3	Azacitidine monotherapy during Week -1 (5 doses), initiate pembrolizumab and epacadostat on C1D1 (after biopsy #2), 5 doses of azacitidine will be administered in Cycles 2 and 3.	Biopsy #1 at baseline. Biopsy #2 on C1D1 (window Day -5 to C1D1, biopsy before pembrolizumab/epacadostat administration). Biopsy #3 during Week 5 or 6.	HNSCC (5-8) Melanoma (5-8) UC (5-8) MSS CRC (5-8)
Expansion Group A-4	Pembrolizumab and epacadostat for 1 cycle, initiate azacitidine after biopsy #2, 5 doses of azacitidine will be administered in Cycles 2 and 3.	Biopsy #1 at baseline. Biopsy #2 on C2D1 (window C1D20 to C2D1, biopsy before azacitidine administration). Biopsy #3 during Week 8 or 9.	HNSCC (5-8) Melanoma (5-8) UC (5-8) MSS CRC (5-8)
Expansion Group A-5	Pembrolizumab monotherapy for 1 cycle, initiate epacadostat and azacitidine after biopsy #2, 5 doses of azacitidine will be administered in Cycles 2 and 3.	Biopsy #1 at baseline. Biopsy #2 on C2D1 (window C1D20 to C2D1, biopsy before epacadostat/azacitidine administration). Biopsy #3 during Week 8 or 9.	First-line melanoma (10)

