5.2. Treatment Groups

This is an open-label, multicenter, Phase 1/2 study evaluating the addition of an epigenetic priming regimen to an immunotherapy doublet in subjects with advanced or metastatic solid tumors. The study will be conducted in 2 parts.

Due to the stop of study enrollment, only subjects in Treatment Group A have been enrolled into Parts 1 and 2. Data from Parts 1 and 2 for Treatment Group A will be summarized together by dose level. The dose levels for Treatment Group A are shown in [Table 1](#).

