5.3.2. Safety Population

The safety population includes all subjects enrolled in the study who received at least 1 dose of study drug (epacadostat, pembrolizumab, or azacitidine). All safety analyses will be conducted using the safety population.

Specific safety analysis populations to be used for study drug-specific tables include the following subgroups:

- Epacadostat safety population
- Pembrolizumab safety population
- Azacitidine safety population

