3.2 Adverse Events				
3.2.1	Overall Summary of Treatment-Emergent Adverse Events	Safety	X	X
3.2.2	Summary of Treatment-Emergent Adverse Events by MedDRA System Organ Class and Preferred Term	Safety	X	X
3.2.3	Summary of Treatment-Emergent Adverse Events by MedDRA Preferred Term in Decreasing Order of Frequency	Safety	X	X
3.2.4	Summary of Treatment-Emergent Adverse Events by MedDRA System Organ Class, Preferred Term, and Maximum Severity	Safety	X	

Table No.	Title	Population	Standard	In-Text
3.2.5	Summary of Grade 3 or 4 Treatment-Emergent Adverse Events by MedDRA System Organ Class and Preferred Term	Safety	X	X
3.2.6.1	Summary of Epacadostat Treatment-Related Adverse Events by MedDRA System Organ Class and Preferred Term	Epacadostat Safety	X	
3.2.6.2	Summary of Pembrolizumab Treatment-Related Adverse Events by MedDRA System Organ Class and Preferred Term	Pembrolizumab Safety	X	
3.2.6.3	Summary of Azacitidine Treatment-Related Adverse Events by MedDRA System Organ Class and Preferred Term	Azacitidine Safety	X	
3.2.7	Summary of Treatment-Emergent Adverse Events With a Fatal Outcome by MedDRA System Organ Class and Preferred Term	Safety	X	X
3.2.8	Summary of Serious Treatment-Emergent Adverse Events by MedDRA System Organ Class and Preferred Term	Safety	X	
3.2.9	Summary of Serious Treatment-Emergent Adverse Events by Preferred Term in Decreasing Order of Frequency	Safety	X	X
3.2.10	Summary of Nonserious Treatment-Emergent Adverse Events by MedDRA System Organ Class and Preferred Term	Safety	X	
3.2.11.1	Summary of Treatment-Emergent Adverse Events Leading to Epacadostat Dose Reduction by MedDRA System Organ Class and Preferred Term	Epacadostat Safety	X	
3.2.11.2	Summary of Treatment-Emergent Adverse Events Leading to Azacitidine Dose Reduction by MedDRA System Organ Class and Preferred Term	Azacitidine Safety	X	
3.2.12.1	Summary of Treatment-Emergent Adverse Events Leading to Epacadostat Dose Interruption by MedDRA System Organ Class and Preferred Term	Epacadostat Safety	X	
3.2.12.2	Summary of Treatment-Emergent Adverse Events Leading to Pembrolizumab Dose Interruption by MedDRA System Organ Class and Preferred Term	Pembrolizumab Safety	X	
3.2.12.3	Summary of Treatment-Emergent Adverse Events Leading to Azacitidine Dose Interruption by MedDRA System Organ Class and Preferred Term	Azacitidine Safety	X	

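### The SAP's DLT percentage uses the pooled Part 1 and Part 2 safety population, so it is not comparable with the 1/6 or 2/9 rule that defines the MTD

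*SAP*

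**What the plan says.** **The row and its denominator.** SAP 8.2.5 lists "Number (%) of subjects reporting any DLTs" among the items of the overall adverse event summary by dose level. Appendix A carries that summary as Table 3.2.1, "Overall Summary of Treatment-Emergent Adverse Events", and assigns it to the Safety population. SAP 5.3.2 states: "The safety population includes all subjects enrolled in the study who received at least 1 dose of study drug". It adds: "All safety analyses will be conducted using the safety population". SAP 5.2 sets the pooling: "Data from Parts 1 and 2 for Treatment Group A will be summarized together by dose level".

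**The decision rule.** SAP 3.1.2 counts DLTs among subjects who received at least 75% of planned doses in the 21-day window (Group A: 4 azacitidine, 32 epacadostat and 1 pembrolizumab dose) "or have had a DLT to be evaluable for dose tolerability". It also lets the investigators and medical monitor assess subjects somewhat under 75% for DLT determination when epacadostat was held for overlapping toxicity. SAP 8.2.3 defines the MTD, for Part 1, as the highest level with at most 1/6 or 2/9 subjects having a DLT. SAP 5.3 defines only a response evaluable and a safety population.

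**The window.** Protocol 5.4.1.1 says that "decisions will be made based on events that are observed from the first day of study drug administration" to the end of Cycle 1 (Day 21) for Group A.

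**The sequencing cohorts.** In SAP Table 5, Cohort A-5 receives "Pembrolizumab monotherapy for 1 cycle, initiate epacadostat and azacitidine after biopsy #2". Cohort A-4 receives the pembrolizumab and epacadostat doublet alone in Cycle 1. Cohort A-3 receives azacitidine in Week -1, and then not again until Cycle 2.

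**The concern.** Determining the MTD or maximum tested dose is part of the Part 1 primary objective, and the DLT proportion is the quantity the design uses for it. The only DLT percentage the SAP plans rests on a different set of people. That set includes:

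- Part 1 subjects who were not evaluable for DLTs, whom Protocol 4.3.2 allows to be replaced;
- Part 2 subjects, who played no part in escalation;
- Cohorts A-3, A-4 and A-5, none of which receives the standard Cycle 1 triplet.

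A reader of the study report would naturally set the printed percentage beside 1/6 or 2/9, but the two measure different things. No other output supplies the right denominator. SAP 8.2.2 and Listing 2.7.3 list DLTs by dose level without an evaluable count, and no population flag exists from which to take one.

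**Working it through.** **1. What the rule is built on.** With p the true DLT rate and q = 1 − p, the 3 + 3 + 3 algorithm escalates on 0/3, 1/6 or 2/9, so

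P(de-escalate) = 1 − [q³ + 3pq²(q³ + 3pq²·q³)].

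At p = 0.20, q³ = 0.512 and 3pq² = 0.384. The bracket is 0.512 + 0.384 × (0.512 + 0.384 × 0.512) = 0.7841, which gives 21.6%. At 30, 40, 50 and 60% the formula gives 43.9, 65.0, 81.1 and 91.2%. All five match Protocol Table 55. The rule therefore works on evaluable cohorts of 3, 6 or 9, and no larger denominator enters it.

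The evaluability counts are also consistent with the plan: 0.75 × 5 = 3.75, rounded up to 4 azacitidine doses; 0.75 × 42 = 31.5, rounded up to 32 epacadostat doses.

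**2. Effect of pooling if a Part 1 DLT exists.** The documents give no pooled DLT percentage and no actual Part 2 numbers by dose level, so this step is an illustration. It assumes that the added subjects were treated at the same dose level and have no DLT recorded. Planned sizes are 10 for A-5 and 25 for A-4. The formula is x/n against x/(n + added).

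| Part 1 evaluable | + A-5 (10) | + A-4 and A-5 (35) |
|---|---|---|
| 1/6 = 16.7% | 1/16 = 6.25% | 1/41 = 2.4% |
| 2/9 = 22.2% | 2/19 = 10.5% | 2/44 = 4.5% |

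**3. Effect of the 75% rule alone.** Adding 1, 2 or 3 non-evaluable Part 1 subjects to 2/9 gives 2/10 = 20.0%, 2/11 = 18.2% and 2/12 = 16.7%.

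**4. Effect with no DLTs.** Protocol 1.8.6 reports none so far in Cohorts 1, 2A, 2B and 3. The percentage is then 0% on any denominator, provided that no DLT is recorded in Part 2. What changes is how much reassurance the zero seems to carry. The exact two-sided 95% upper limit for zero events is 1 − 0.025^(1/n):

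- 0/6: 45.9%; with A-5 added, 0/16: 20.6%; with A-4 and A-5 added, 0/41: 8.6%.
- 0/9: 33.6%; with A-5 added, 0/19: 17.6%; with A-4 and A-5 added, 0/44: 8.0%.

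The SAP plans no interval for DLTs, so these limits show what a reader might infer. They are not planned output.

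**The case against.** The strongest reply is that nothing turns on this row. Escalation follows the 3 + 3 + 3 rule on evaluable subjects and is settled in cohort-review teleconferences (Protocol 5.4.1.1.3, SAP 9). SAP 8.2.3 confines the MTD definition to Part 1. The Part 1 primary endpoint is adverse events, examinations, vital signs, ECGs and laboratory tests, not this percentage. DLTs are also listed, and SAP 8.1 allows sparse tables to become listings. All of this stands, and it limits the point to reporting.

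A reader might go further and infer that the reported DLT rate is diluted and that the triplet is made to look better tolerated than it was. The documents do not support that, for three reasons:

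- Dilution needs at least one DLT, and Protocol 1.8.6 reports none in Part 1 to date.
- The direction is not fixed. Cohorts A-1 and A-2 receive all three drugs from Cycle 1 Day 1 (Protocol Table 29), and Protocol 5.4.1.1 does not restrict the DLT definition itself to Part 1. If DLTs are recorded in Part 2, pooling could raise the percentage. The documents do not say whether they are.
- Enrollment stopped early, and neither the expanded dose level nor the numbers treated at it are given.

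The 75% component is also small. Protocol Table 10 makes failure to receive 75% because of toxicity a DLT in itself, subject to listed exceptions, so the rule mainly removes subjects who were short of doses for other reasons.

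The objection does not remove the mismatch. Followed as written, the SAP prints a percentage that is not the one its own rule uses, and it gives the reader no denominator with which to correct it.

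**Conclusion.** The denominator is mis-specified, and the point is minor because it affects reporting only. The planned DLT percentage is not comparable with the 1/6 or 2/9 criterion at any dose level that Part 2 subjects or non-evaluable Part 1 subjects enter. It would be diluted at an expanded level only if a Part 1 DLT occurred there and the added subjects have none recorded. In that case 22.2% could print as 10.5% with A-5 alone, on planned numbers. On the zero Part 1 DLTs reported to date, the Part 1 figure is 0% whichever denominator is used, and the fault lies in the apparent precision of the larger one. There is no ground for saying that an MTD or dose choice was affected, or that tolerability was misstated in a known direction.

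**What to change.** 1. In SAP 5.3, add a DLT-evaluable population: Part 1 dose-escalation subjects who met the 75% rule, had a DLT, or were assessed for DLT determination under the below-75% provision of SAP 3.1.2. The last group is needed so that the set matches the subjects actually used in escalation decisions.
2. In SAP 8.2.2 and 8.2.5, compute the DLT number and percentage on that set by Part 1 dose level, and remove the row from the pooled Table 3.2.1.
3. List the Part 1 subjects excluded from the set, with doses received and reason.
4. State whether DLTs are recorded in Part 2. If they are, report them separately, noting that A-3, A-4 and A-5 do not receive the standard Cycle 1 triplet.

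The cost is one population definition, one moved row and one short listing. Study drug administration and DLTs are already planned listings (2.7.1 and 2.7.3). The downside is smaller and less reassuring denominators.
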